**Study Protocol: Emotion-Diet Interactions in Pregnancy**

**NCT04430439**

**Date of Document: 10/20/2022**

**C.1 Overview.** This research will represent the first investigation of objectively measured diet-stress interactions in human pregnancy, thus providing critical insight to the contribution of psychosocial stress in influencing important gestational metabolic pathways that have implications for maternal and child health and disease risk. The working hypothesis is that acute psychosocial stress will exacerbate the postprandial plasma glucose/insulin and free fatty acid (FFA) response to a standardized meal, and that this response will be exaggerated after consumption of a high GI versus a low GI meal. The overall strategy is to enroll a cohort of non-diabetic pregnant women with overweight and obesity to test the postprandial metabolic response to a standardized meal of varying GI, with and without psychosocial stress exposure.

**C.2 Study Design.** This is a two-armed, randomized, cross-over study in which N=80 women will be randomly assigned in a parallel design to either a low or high GI standardized breakfast. Within each arm, N=40 women will attend two test study visits in a randomized, cross-over design, to undergo either the TSST challenge task or a control non-stress task immediately following consumption of their assigned meal type.

**C.3 Clinical Research Setting.** The study will be performed at the PI's research facility on the UCI campus in Irvine and will utilize additional clinical facilities of the UCI Institute of Clinical and Translational Science (ICTS).

**C.4 Study Site and Population.** Subjects will be primarily recruited from UCI-affiliated clinics; the UCI Medical Center faculty private practice, and UCI-affiliated family health clinics in surrounding districts within Orange County, CA, which serve women from an urban metropolitan area encompassing a population base of over 2.75 million residents. Recent demographic profiles of this population indicate that 68% of the patients are multiparous; 65% are married, and 58% belong to ethnic minority groups (predominantly Hispanic). Over the past year, the PI has independently enrolled N=33 Hispanic women from this prenatal population.

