**C.6.4 Experimental stress/non-stress paradigm:** The TSST is a standardized, validated experimental procedure to effectively induce psychosocial stress among healthy adults, including pregnant women. The TSST takes 15 mins to complete and involves a 5 min speech preparation, 5 min speech performance under stern observation of an evaluative committee while being video-taped, and 5min complex verbal arithmetic task. For the control non-stress condition, women will have a relaxed 15 min conversation with a familiar researcher.

**C.6.5 Test meal composition:** Test meals will be prepared by research staff under direction of the study PI, a registered dietitian. Both types of test meals will have comparable caloric content but will vary in fiber, carbohydrate and fat content to alter the GI value (*Table 1*). The pre-visit standard evening meals will have a medium GI value. All participants will be asked about food allergies or intolerances and the meals will be adapted as appropriate, while maintaining an equivalent energy content and macronutrient distribution.

**Table 1:** approximate nutritional composition of standard evening and test visit meals

	Standard pre-visit evening meal	Low GI test meal	High GI test meal
Energy, kcal	600	300	300
% carbohydrate	55	47	76
% protein	15	19	13
% fat	30	33	12
Fiber, g	15	4.5	0.7

**C.6.6 Bio-sample processing and analysis:** Fasting and postprandial blood samples will be centrifuged at 1500rpm for 15min and the separated plasma aliquoted to microtubes. All plasma and saliva will be stored at -80°C until analysis. Plasma will be assayed for glucose and insulin and saliva for cortisol by ELISA. Plasma FFA will be measured by LC-MS/MS. HOMA-IR will be computed from fasting glucose and insulin values and Adipo-IR from fasting insulin and FFA values. The AUCglu/ins and AUCFFA will be determined for each visit.

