**C.6.7 Randomization procedures:** A biostatistician will generate the randomization sequence for a 1:1 assignment to the meal group arms (*i.e.* high GI or low GI), and for the sequence of stress or non-stress protocols at the test study visits (*i.e.* stress at v1 and non-stress at v2, or non-stress at v1 and stress at v2) within each arm. Randomization sequences will be contained in sealed, opaque envelopes labeled by sequential study IDs and only revealed by research coordinators after completion of a screening visit for a fully eligible participant.

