Statistical Analysis Plan: Emotion-Diet Interactions in Pregnancy (PREDIP)

NCT04430439

Date of document: 4/6/2020

STATISTICAL DESIGN AND POWER ANALYSIS

Statistical Design: The statistical approach for each of the Specific Aims will be performed as follows:

Aim 1a: A cross-over study design will test the hypothesis that experimental exposure to a standardized psychosocial stress task will potentiate the postprandial metabolic response to the standardized meal. Each subject will represent her own control within the assigned meal group (low or high GI). A paired-samples t-test will be employed, using the model: $E[Y_i] = \Delta AUC_i = (AUC_i)v1 - (AUC_i)v2$

where Y_i denotes the outcome measurement (change in $AUC_{glu/ins}$ or AUC_{FFA}) on maternal i, and AUC_i denotes the AUC for either metabolic outcome at a given laboratory visit; v1 or v2. As such, a test of the hypothesis that the above equations equals 0, represents a test that the effect of acute psychosocial stress exposure does not moderate the postprandial response to a standardized meal. A sensitivity analysis to estimate the difference in response by randomization sequence will ensure that the order of protocols does not confound the results.

Aim 1b: To explore the difference in the postprandial metabolic response following acute psychosocial stress exposure across meal types (low vs high GI), an independent sample t-test will be employed to compare the mean $AUC_{glucose/insulin}$ between the high GI and low GI groups.

Aim 2: To determine whether individual variation in biological stress reactivity (i.e., $AUC_{cortisol}$ and AUC_{HRV}) moderates the effect of acute psychosocial stress on the metabolic response to the standardized meal, a general linear model accounting for within subject correlation will be employed, according to the model:

$$E[Y_{ij}] = \beta_0 + \beta_1 STRESS_{ij} + \beta_2 REACT_{ij}$$

where Y_{ij} denotes the outcome change in the AUC_i on maternal i, STRESS denotes the condition of exposure (stress vs no stress) to mother i on laboratory visit j, and REACT denotes stress reactivity, measured by $AUC_{cortisol}$ or AUC_{HRV} . A test of $H_0: \beta_1 = 0$ will test the hypothesis that mean AUC_i ($AUC_{glu/ins}$ and AUC_{FFA}) differs by stress condition after adjustment for stress reactivity. An exchangeable correlation matrix will be assumed in the model.

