Power Analysis: The primary outcome of the proposed research is the difference in the postprandial glucose/insulin response to a standardized meal (of either low or high GI) between the stress and non-stress conditions. Utilizing a cohort of 40 women in each meal group, it is estimated that the proposed study will have approximately 80% power to detect a 0.44 standard deviation difference in the mean within subject change in postprandial metabolic response ($AUC_{glu/ins}$ and AUC_{FFA}), associated with the introduction of the stress paradigm.

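### Aim 1b compares post-stress AUC between meal groups rather than the stress-induced change, so the hypothesised meal-by-stress interaction is never tested

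*SAP*

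**What the plan says.** Protocol C.1 presents the trial as the "first investigation of objectively measured diet-stress interactions in human pregnancy". Its working hypothesis has two parts: stress worsens the postprandial glucose/insulin and FFA response, and "this response will be exaggerated after consumption of a high GI versus a low GI meal".

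The SAP assigns the meal comparison to Aim 1b, whose purpose is "To explore the difference in the postprandial metabolic response following acute psychosocial stress exposure across meal types (low vs high GI". The method is that "an independent sample t-test will be employed to compare the mean" glucose/insulin AUC of the high GI and low GI groups. FFA is not named.

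The other analyses are:

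- **Aim 1a:** "A paired-samples t-test will be employed, using the model" of ΔAUC, the difference between a woman's two visits. Its sensitivity analysis concerns the order of the two tasks.
- **Aim 2:** a linear model with an intercept, a stress-condition term and a reactivity term.
- **Power Analysis:** "The primary outcome of the proposed research is the difference in the postprandial glucose/insulin response to a standardized meal" between the stress and non-stress conditions, with 40 women per meal group.

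**The concern.** The second part of the hypothesis says that the stress effect is larger in one arm than in the other. Testing it requires each woman's stress visit to be set against her own non-stress visit, and the resulting changes to be compared between arms. Aim 1b, as worded, takes the response after stress and ignores the non-stress visit.

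The two meals are built to produce different responses. Protocol C.6.5 says that they "will vary in fiber, carbohydrate and fat content to alter the GI value", and Table 1 gives approximate values of 76% against 47% carbohydrate and 0.7 g against 4.5 g fiber, at 300 kcal each. A difference in glucose or insulin AUC between arms is therefore plausible with no stress at all. A significant Aim 1b result could then be reported as support for a diet-stress interaction when it requires neither an interaction nor any stress effect.

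**Working it through.** **1. What each analysis estimates.** Let M be the high-minus-low meal difference in mean AUC at the non-stress visit, S the stress effect in the low GI arm, and S + I the stress effect in the high GI arm. The hypothesis concerns I.

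- Stress-visit AUC, high minus low: (M + S + I) − S = M + I.
- AUC averaged over both visits, high minus low: M + I/2.
- Stress-minus-non-stress change, high minus low: (S + I) − S = I.

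Only the third isolates I. Aim 1a estimates S or S + I within an arm and makes no comparison between arms. Aim 2 has no meal term and no product term.

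**2. The plan's own power figure.** Inputs are n = 40 per meal group and 0.44 SD of the within-woman change (SAP, Power Analysis). The significance level is not stated; two-sided 0.05 is assumed throughout. Normal approximation for a paired test: Φ(√40 × 0.44 − 1.960) = Φ(0.823) = 79.5%. The noncentral t gives about 77%. The stated figure of about 80% reproduces and is not in dispute. It covers the stress contrast within one meal group, not Aim 1b.

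**3. Aim 1b as written, with I = 0.** Two-sample t-test, 40 per arm, noncentral t with noncentrality d√(40/2), where d = M in SDs of AUC (assumed):

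| M (SD of AUC) | Aim 1b significant |
|---|---|
| 0.2 | 14.3% |
| 0.5 | 59.8% |
| 0.8 | 94.2% |
| 1.0 | 99.3% |

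In simulations of 20,000 trials with M between 0.2 and 1.0 SD and I = 0, the t-test on the change rejected in 4.8% to 5.2% of trials. M cancels from the change.

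**4. Power for a true interaction.** With equal AUC variance at both visits and within-woman correlation ρ (both assumed), the SD of the change is √(2(1 − ρ)) in AUC-SD units. For I = 0.5 AUC-SD and M = 0:

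| ρ | SD of change | Standardised effect | Power, change score | Power, as written |
|---|---|---|---|---|
| 0.3 | 1.183 | 0.5/1.183 = 0.42 | 46% | 60% |
| 0.5 | 1.000 | 0.50 | 60% | 60% |
| 0.7 | 0.775 | 0.5/0.775 = 0.65 | 81% | 60% |

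The change score gains power only above ρ = 0.5, so the argument for it is validity, not power.

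**5. Masking.** If M = +0.5 SD and I = −0.5 SD, then M + I = 0. The written test rejects about 5% of the time, while the change score keeps the power shown in step 4 (46%, 60% or 81%). This needs a meal effect and an interaction of opposite sign.

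**6. What the correct test can detect at 40 per arm.** In SDs of the change:

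- Detectable difference at 80% power: (1.960 + 0.842) × √(2/40) = 0.626 by the normal approximation, 0.634 by the t distribution. In AUC-SD units this is 0.634 × 1.183 = 0.75, 0.63, or 0.634 × 0.775 = 0.49 at ρ = 0.3, 0.5 or 0.7.
- Power at a difference of 0.44 SD: 50.3% (normal), 49.3% (t).
- Women per arm for 80% power at 0.44 SD: 2 × (2.802/0.44)² = 81.1, so 82 (normal); 83 by the t distribution.

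**The case against.** The strongest objection concerns the reading. The clause that specifies the t-test names no visit, and the SAP is loose with its notation: Aim 2 calls its outcome a change in AUC but states its hypothesis in terms of mean AUC. Aim 1b follows an aim whose outcome is a change, so the authors may have meant ΔAUC. That is possible, but the text does not say so. It refers to the response after stress and writes plain AUC. If ΔAUC was intended, the same one-line correction is needed. Pooling both visits would not rescue the test either, since it estimates M + I/2.

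Other points stand in part:

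- Aim 1b is worded as exploratory, and the primary stress versus non-stress comparison does not depend on it. Both are true. The label does not change which quantity is estimated, and the interaction is half of the working hypothesis.
- Aim 1a can be run within each arm, which gives the two components of the interaction. It does, but no comparison of the two is planned, and finding significance in one arm and not the other is no test of a difference.
- The rejection rates in step 3 are not type I errors for the literal question of whether post-stress AUC differs by meal. Correct: they become errors only if the result is read as evidence of interaction. Given the hypothesis in C.1, that reading is a real risk.
- The replacement test has modest power, and below ρ = 0.5 it has less power than the written test has when there is no meal effect. This is true and should be disclosed, but it does not justify a test of a different quantity.

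**Conclusion.** The concern holds. As worded, Aim 1b estimates the effect of the meal under stress, and no analysis in the SAP tests whether the stress effect differs by meal. This follows from the definition of the contrast and needs no numerical assumption. The size of the problem depends on the meal effect without stress, which the documents do not give. Over assumed values of 0.2 to 1.0 SD of AUC, Aim 1b would be significant in 14% to 99% of trials with no interaction, against 5% for a test on the change. Masking of a real interaction is possible but needs opposite signs and is the lesser worry. The primary comparison and its stated power are untouched. The wording should be corrected before Aim 1b is analysed, because it determines what the trial can conclude about diet-stress interaction.

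**What to change.** Replace the Aim 1b test with an independent-samples t-test between meal groups on each woman's AUC at the stress visit minus her AUC at the non-stress visit, for glucose, insulin and FFA. Define the difference by condition and do not reuse the v1-minus-v2 form of Aim 1a. Protocol C.6.7 randomizes the order ("stress at v1 and non-stress at v2, or non-stress at v1 and stress at v2"), so under a visit-based difference women who have the control task first would contribute with the opposite sign. An alternative is a mixed model with meal, condition, meal × condition and period, testing meal × condition. Report the post-stress AUC comparison as descriptive only. The exploratory label can stay if that is the intention.

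The cost is SAP wording. Every woman attends both conditions on the same meal (Protocol C.6.3), so no new visits or data are needed. The SAP gives no power for this aim, so no stated figure changes. It should, however, say that 40 per arm gives 80% power only for a between-meal difference of about 0.63 SD of the within-woman change, so that a null result is not read as absence of an interaction.

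### SAP Aim 2 defines its outcome as a between-visit change in AUC, while its stress covariate, correlation structure and hypothesis need the AUC at each visit

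*SAP*

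**What the plan says.** The Aim 2 model in the SAP has an intercept, a STRESS term (beta1) and a REACT term (beta2), all indexed by woman i and visit j. The sentence under the model then says that Y_ij "denotes the outcome change in the AUC_i on maternal i". The SAP defines a change in AUC in only one place, Aim 1a, where the formula ends "AUC_i)v1 - (AUC_i)v2" and the result is indexed by woman alone.

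The rest of the Aim 2 paragraph works at visit level:

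- The covariate: "STRESS denotes the condition of exposure (stress vs no stress) to mother i on laboratory visit j".
- The correlation: "An exchangeable correlation matrix will be assumed in the model".
- The only test named, beta1 = 0, is said to examine whether "mean AUC_i ($AUC_{glu/ins}$ and AUC_{FFA}) differs by stress condition after adjustment for stress reactivity".

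The opening sentence of Aim 2 gives a different purpose: to find out whether reactivity moderates the effect of stress. The model has no STRESS-by-REACT term.

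**The concern.** A visit 1 minus visit 2 change has already used up both visits, so each woman contributes one number. STRESS takes both of its values within every woman, because each attends one stress visit and one control visit (Protocol C.2 and C.6.3). An outcome that is constant within a woman cannot show a contrast that exists only within her.

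The sentence that defines the outcome is the one an analyst would use to build the dataset. One reading of the paragraph gives a usable stress contrast and the other gives none, and beta1 is the only coefficient for which Aim 2 names a test. The choice should be settled in the text before analysis.

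**Working it through.** **Inputs.** From the SAP: the Aim 1a change, the Aim 2 model and its definitions, and the Power Analysis figures (40 women per meal group, 0.44 SD, about 80% power). From the Protocol: both conditions in every woman. Assumed, because the documents do not give them: two-sided alpha 0.05; SD of the within-woman difference equal to 1; REACT raised by 1 unit under stress; a moderation slope of 0.5 where stated.

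**1. The plan's own figure.** Power = Φ(0.44 × √40 − 1.96) = Φ(2.783 − 1.960) = Φ(0.823) = 79.5%, which agrees with the stated figure. The exact paired t calculation gives about 77.5%. This is the paired comparison of Aim 1a; the SAP gives no power figure for Aim 2.

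**2. The literal outcome.** *One row per woman:* the row has no visit index and spans both conditions, so it contains no stress-control contrast and beta1 cannot be estimated.

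*Change repeated on both rows:* least squares with an intercept and a binary STRESS makes the residuals average zero within each condition. Hence

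beta1 = [mean Y under stress − mean Y under control] − beta2 × [mean REACT under stress − mean REACT under control].

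With Y_i1 = Y_i2 the first bracket is 0. So beta1 = 0 without REACT, and beta1 = −beta2 × (REACT gap) with it. This step needs none of the assumed values.

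**3. Numerical check.** 80 women, 500 simulated trials per setting, REACT in the model, least squares with standard errors clustered by woman. Cells show mean beta1 and the share of trials with p < 0.05.

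| True stress effect (SD) | Repeated change, stress − control | Repeated change, v1 − v2 | Visit-level AUC |
|---|---|---|---|
| 0 | −0.005; 5.8% | 0.003; 6.4% | 0.010; 6.2% |
| 0.44 | −0.002; 7.2% | −0.005; 4.4% | 0.439; 83.2% |
| 1 | −0.002; 4.2% | −0.004; 3.4% | 0.995; 100% |
| 2 | 0.001; 3.8% | −0.001; 5.0% | 2.010; 100% |
| 0.44, moderation slope 0.5 | −0.230; 51.8% | −0.008; 5.2% | 0.199; 24.8% |

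With REACT left out, beta1 on a repeated change was 0 to rounding error in every dataset. With 40 women, the visit-level model at 0.44 SD gave a mean of 0.451 and 57.0% rejection.

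**4. The specified correlation.** One exchangeable fit to a repeated change (40 women) estimated the correlation at 1.03 without REACT, with an undefined standard error for beta1, and at 1.04 with REACT. Neither is an admissible correlation.

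**5. What the visit-level outcome delivers.** In the last row of the table, beta1 averages 0.199 against a true mean effect of 0.44. STRESS alone averaged 0.433 in the same runs, and the difference, 0.433 − 0.199 = 0.234, is the part taken up by beta2 × (REACT gap). So beta1 is a REACT-adjusted contrast and not the whole stress effect.

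For moderation, let R_i be one reactivity value per woman and add beta3 × STRESS × R_i. Subtracting control from stress within a woman leaves beta1 + beta3 × R_i. A regression of the stress-minus-control change on R_i, one row per woman, therefore targets the same beta3.

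**The case against.** The strongest reply is that the visit-level AUC is plainly what was meant. The outcome carries the subscript ij, the model is described as allowing for within-subject correlation, the hypothesis concerns mean AUC, Aim 1a defines AUC_i as the AUC at a given visit, and Protocol C.6.6 determines the AUCs for each visit. On this view the word *change* is a carry-over from Aim 1a. This largely stands. A reader might infer that Aim 2's stress test must return zero or an artefact whatever stress does; the documents do not support that, because it holds only for the outcome as literally defined.

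It is also fair that a literal exchangeable fit would fail visibly (step 4). The least-squares rejection rates for a repeated change illustrate the algebra; they do not predict the planned analysis. The size of the artefact under moderation depends on the assumed slope and REACT gap.

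Two further inferences go too far. One is that a change score can never serve Aim 2: a stress-minus-control change with one row per woman is a direct route to moderation. The other is to judge the repair by the power of a model with STRESS alone. The SAP keeps REACT in the model, so the like-for-like figures are those in the last column of the table.

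What remains is that the defining sentence names a variable which the model cannot use, and the subscript on the disputed symbol does not settle its definition.

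**Conclusion.** The point holds as an internal contradiction in Aim 2's outcome definition. Under the literal definition, beta1 is either not estimable, or 0, or −beta2 × (REACT gap); this is algebra and rests on no assumed value. Under the visit-level reading, beta1 is estimable and, without moderation, follows the true effect (0.439 for a true 0.44 SD with 80 women). Its 83% rejection rate there, and 57% with 40 women, depend on the assumptions listed. The SAP does not say whether Aim 2 pools the meal groups.

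Resolving the contradiction makes the named test match its stated hypothesis. It does not answer the moderation question. The Aim 1a primary comparison and its power statement are not touched by this point.

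**What to change.** In SAP Aim 2, replace the phrase that defines Y_ij with: *the AUC for mother i at laboratory visit j (AUC_ij)*. Outcome, STRESS, REACT and the exchangeable correlation then all refer to visits, and beta1 is the stress-control difference in AUC adjusted for REACT, as the SAP's hypothesis says.

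State in the same place that this model does not test moderation. To test it, either add a STRESS-by-reactivity term to the visit-level model, or regress the stress-minus-control change, one row per woman, on woman-level reactivity. The two are equivalent when reactivity is a single value per woman. If a change score is used, define it by condition, since the only change now defined is by visit order.

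The outcome correction costs one sentence and the moderation test a further term or line. Neither alters data collection, sample size or procedures.

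### Aim 2 asks whether stress reactivity moderates the stress effect, but its additive model and its one named test (beta1 = 0) do not test moderation

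*SAP*

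**What the plan says.** The SAP (Statistical Design, Aim 2) sets out to learn whether "individual variation in biological stress reactivity", meaning cortisol AUC or HRV AUC, "moderates the effect of acute psychosocial stress on the metabolic response to the standardized meal". The model is:

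`E[Y_ij] = beta0 + beta1 STRESS_ij + beta2 REACT_ij`

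with an exchangeable working correlation. The one hypothesis named is H0: beta1 = 0, explained as whether mean AUC "differs by stress condition after adjustment for stress reactivity".

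On the terms of the model:
- STRESS "denotes the condition of exposure (stress vs no stress) to mother i on laboratory visit j".
- "REACT denotes stress reactivity, measured by" cortisol or HRV AUC. The text does not say whether this is one value per woman or one per visit; the subscript ij suggests per visit, while the stated aim suits one per woman.
- Y "denotes the outcome change in the AUC_i on maternal i", although it carries a visit subscript.

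Neither document contains a product term, a test of beta2, a contrast between reactivity subgroups, or any other moderation analysis. The only power figure (SAP, Power Analysis) is for the average within-woman stress effect, with 40 women per meal group.

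**The concern.** Moderation means that the stress effect differs between women according to their reactivity. The planned model does not allow this: its stress effect is beta1 for everyone. The named test therefore asks whether a stress effect remains after adjustment.

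The SAP does not say that rejecting beta1 = 0 will be reported as moderation, so the harm depends on how the result is read. If it is presented as the Aim 2 answer, a stress effect common to all women would look like moderation, and real moderation would not be what was tested. If the mismatch is noticed only at analysis, the choice between beta1, beta2 and an unplanned interaction would be made after the data are seen.

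**Working it through.** **The plan's own figure.** With 40 women and a 0.44 SD within-woman effect, and assuming two-sided alpha 0.05 (the SAP states no alpha), power = Phi(0.44 x sqrt(40) - 1.96) = Phi(2.783 - 1.960) = Phi(0.823) = 79.5%. This reproduces the stated 80% or so. It concerns the average stress effect only.

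**Algebra.** Let D_i be a woman's stress minus non-stress AUC, and R_i her stress minus non-stress cortisol (or HRV) AUC.
- *REACT is one value per woman.* It cancels from the within-woman difference, so E[D_i] = beta1. With complete pairs, the Aim 2 test is simply a test of the average stress effect.
- *REACT is a visit value.* E[D_i] = beta1 + beta2 R_i. Now beta1 is the stress effect with any part running through REACT removed. If the average effect is zero but D_i rises with R_i, and the task raises REACT, then beta1 is pushed below zero.
- *Interaction model.* E[D_i] = b1 + b3 R_i, so b3 measures how the stress effect varies with reactivity. It is the within-woman form of the visit-level beta2.

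**Simulation inputs.** From the SAP: 0.44 SD, and 40 women per arm (80 pooled). Assumed:
- residual SD of D_i is 1, and the between-visit AUC correlation is 0.5;
- non-stress REACT has SD 1;
- the task response in REACT has (mean, SD) of (0, 1), (0.5, 1), (1, 1) or (1.5, 0.7).

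The SAP model was fitted as a Gaussian GEE with exchangeable correlation and a robust z-test. The b3 test was the t-test from regressing D_i on R_i and sequence, plus meal group when n = 80. There were 5,000 replicates per cell, giving a Monte Carlo 95% error of at most 1.4 points. Ranges run over the task responses.

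| Rejection rate | n = 80 | n = 40 |
|---|---|---|
| **Uniform 0.44 SD stress effect, no moderation** | | |
| beta1, one value per woman | 97-98% | 79% |
| beta1, visit-level REACT | 76-97% | 50-79% |
| b3 | 5% | 5% |
| **Moderation 0.4 SD per SD of reactivity, zero average effect** | | |
| beta1, one value per woman | 6% | 6% |
| beta1, visit-level REACT | 6-41% | 7-28% |
| beta2 (no test planned), one value per woman | 55% | 36% |
| beta2 (no test planned), visit-level REACT | 63-81% | 42-57% |
| b3 | 93% | 66% |

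In the visit-level moderation row, nearly all beta1 rejections are in the negative direction once the task raises REACT; mean beta1 falls to -0.30. Varying the between-visit correlation from 0.3 to 0.7 (3,000 replicates) widens the visit-level beta1 range under the uniform effect to 65-98% (80 women) and 43-81% (40).

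**What b3 cannot do.** The 5% for b3 holds when REACT itself has no effect on the outcome. Suppose instead that the 0.44 SD effect runs wholly through reactivity, with no moderation. The slope per SD of R_i is then 0.44 x SD / mean:

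| Task response (mean, SD) | Slope per SD of R_i | b3 rejects, n = 80 | b3 rejects, n = 40 |
|---|---|---|---|
| (0.5, 1) | 0.88 | 100% | 100% |
| (1, 1) | 0.44 | 96% | 74% |
| (1.5, 0.7) | 0.21 | 44% | 24% |

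**Detectable moderation.** For 80% power at two-sided 0.05, the correlation between R_i and D_i must be about tanh(2.80 / sqrt(n - 3)). That is tanh(2.80 / 8.775) = 0.31 for 80 women and tanh(2.80 / 6.083) = 0.43 for 40.

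**The case against.** Four points can be made for the plan.

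1. *The SAP uses the word loosely.* Aim 1a calls a plain paired difference a test of whether stress moderates the meal response. Aim 2 might likewise mean only a stress effect adjusted for reactivity. But Aim 2 names a moderator, an effect and an outcome, which is effect modification. If it meant only that reactivity influences the response, the relevant coefficient would be beta2, which is not tested either.

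2. *Y is described as a change.* If Y were the within-woman difference, beta2 would be the moderation slope. But each woman then has one value, which leaves a visit-varying STRESS term and a within-woman correlation with nothing to do, and the SAP explains its test in terms of mean AUC by condition. On this reading too, the named coefficient is beta1.

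3. *The visit-level model already carries the signal in beta2, and b3 does not isolate moderation.* Both statements are true. They limit what any result can be taken to show, but they do not make beta1 = 0 a moderation test. With exchangeable correlation, beta2 also mixes between-woman and within-woman information and rejects less often than b3 in the simulation.

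4. *The percentages rest on assumptions.* This stands. In particular, the 6% for beta1 assumes a zero average stress effect, contrary to the working hypothesis in Protocol C.1. The gap itself follows from the algebra and needs no simulation.

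**Conclusion.** The concern holds. Aim 2 states a moderation question, and the SAP gives an additive model and one test that does not address it. This is so whether REACT is one value per woman or one per visit. Under the per-woman reading the named test rejects in 97-98% (80 women) or 79% (40) when a 0.44 SD stress effect is uniform, and in 6% when there is moderation without an average effect. Under the visit-level reading beta1 also loses any stress effect running through REACT and can turn spuriously negative. These sizes depend on the assumed task responses, correlations and moderation strength.

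The problem is confined to Aim 2 and should be fixed before analysis. The primary comparison, stated as "The primary outcome of the proposed research is the difference in the postprandial glucose/insulin response to a standardized meal" between stress and non-stress conditions, and its power statement are unaffected.

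**What to change.** Amend Aim 2 in the SAP as follows.
- Define Y_ij as the AUC at visit j.
- Define one mean-centred reactivity value per woman, R_i: cortisol (or HRV) AUC at the stress visit minus that at the non-stress visit.
- Fit `Y_ij = b0 + b1 STRESS + b2 R_i + b3 STRESS x R_i + period + meal group`, and make H0: b3 = 0 the Aim 2 test.
- Carry out the test as the t-test from regressing D_i on R_i, sequence and meal group. Sequence carries the period effect. Meal group there acts as a STRESS-by-meal term, which is optional and not part of the error.
- State that the meal arms are pooled, and give the detectable correlation (about 0.31 with 80 women, 0.43 with 40).
- State that b3 shows only whether the stress effect varies with reactivity. It cannot separate moderation from mediation and must not be reported as proof of moderation.

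The cost is wording. Saliva and HRV are already collected at both visits (Protocol C.6.2 and C.6.3), so R_i needs no new data. The downsides are the fairly large correlation needed for 80% power and the limit on interpretation.
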